3.10 Conduct of the Study

There will be 3 phases to the conduct of this study as below:

- Phase 1 Adaptation, Validation and Translation of the Questionnaire,
Educational Booklet and Intervention Module**
- Phase 2 Pretest and Pilot test of the study**
- Phase 3 Implementation of the study (Field Work)**

The conduct of the study will be discussed in detailed manner according to the phases of the study.

3.10.1 Phase 1 Adaptation, Validation and Translation of the Questionnaire, Educational Booklet and Intervention Module

In Phase 1, there are 3 components that will undergo the adaptation; namely the baseline and follow-up questionnaire, educational booklet and intervention module. The details of these 3 components are described below in 6.10.1.1 till 6.10.1.3.

BENIT trial (Paulino YC et al., 2020) was selected as the intervention of choice to be cross-culturally adapted in Malaysia due to few reasons. Firstly, this is the first intervention of its kind that targets primarily the users of betel quid in an indigenous population that utilises areca nut. Other researches focusses more on smokeless tobacco. As Malaysian high risk community are more common to use areca nut singly and mostly without smokeless tobacco, thus BENIT was selected to be adapted in Malaysia for this study. There are other studies too from Pakistan that focusses on adolescents. Since the population that chews betel quid in Malaysia are above 40 years old, thus BENIT again was a more appropriate intervention to be adapted in Malaysian high risk community.

3.10.1.1 Baseline & Follow- up Questionnaire

A structured questionnaire (Appendix C) will be used in this study. The questionnaire will be adapted from the BENIT trial (Paulino YC et al., 2020). In the **baseline survey**, questions regarding demographics, BQ chewing behaviours, BQ composition, BQ dependency level, reasons for chewing, readiness and self-perceived barriers to quit will be asked.

On the 22-day, 1-month and 3-month, a follow-up questionnaire will be prepared. Information consisting of intervention compliance (whether they had attempted to quit chewing since start of the intervention), current chewing status (current chewer or ex-chewer), how much the participants had cut down on their chewing (quids/day), how many group sessions the participants attended (as well as reasons for absent if missed any sessions) and BQ composition if the participants are still chewing.

Several composite questions from other validated questionnaire will be added to existing questionnaire set to achieve a strategic fit to meet the objective of this study; BQ composition (Tahir Z & Doss JG, 2003), BQ dependency level (Herzog TA et al., 2014), reason for chewing (Little MA et al., 2014), readiness and self perceived barriers in ceasing the habit (Maling TH, 2016 & Brown RA, 2003).

Prior to formulation and adaptation of the questionnaire, permission to use and modify the established questionnaire will be obtained from original author (Paulino YC et al., 2020).

Below are the summaries,

The baseline questionnaire (Appendix C) will be comprised of:

- a) Section A – to obtain demographics information of the study participants
- b) Section B – to assess the BQ chewing behaviours (including chewing history)
- c) Section C – to assess BQ composition used by the participants
- d) Section D – to assess the BQ dependency level
- e) Section E – to assess the reason for betel quid chewing
- f) Section F – to assess the readiness and self perceived barriers to quit habit

The follow up questionnaire (Appendix M) (22-day, 1-month & 3-month) :

- a) Section A – brief personal particulars of the participants
- b) Section B – to assess participant’s compliance towards the intervention by assessing the total number of session attended and reasons if absent
- c) Section C – to assess the current chewing status
- d) Section D – to assess number of cut-down of habits by the participants (quid/day)
- e) Section E – to assess BQ composition (if still chewing)

3.10.1.2 Educational booklet

The educational booklet is a single booklet that will consist of a minimal intervention designed to encourage participants to quit BQ behaviour. This educational booklet will be adapted from the one used in the BENIT trial (Paulino YC et al., 2020) (Figure 3.3). The booklet will serve to provide general information regarding AN and BQ, risk associated with BQ chewing behaviour through captivating graphical aids, cessation strategies that are modeled after tobacco cessation and researcher’s contact information to the participants. Both study groups will receive an educational booklet.

Cessation strategies will be designed in a heuristic manner. Heuristics are mental shortcuts that assist people to solve problems and make judgements quickly and efficiently (Marewski JN & Gigerenzer G, 2012). These strategies will shorten the decision-making time and allow participant to reduce risk habits without frequently stopping or procrastinating about their next reduction actions.

[figure not shown]

Figure 3.3 BENIT's Educational Booklet

3.10.1.3 Intervention module

The intervention module will be adapted from the one used in the BENIT trial (Paulino YC et al., 2020) and will consist of 7 worksheets as illustrated in Figure 3.4. This worksheet serves to guide participants to quit BQ chewing behaviour by increasing their understanding of the group session intervention and by increasing their self-efficacy in their quitting journey. All worksheets are explained in this section and are attached in the Appendix.

[figure not shown]

Figure 3.4 Summary of Intervention Module Worksheets

Trigger monitoring logs (Appendix D) are a personalised written records of the participant's triggers, the different types of triggers they experienced and the many varied situations that triggers them to chew. Common examples such as urge to chew after a meal or after meeting a close friend will be given to aid their comprehension and to obtain a more accurate data. The log will contain a record of the number of quids chewed in a day, the situation and mood that they were in prior they initiated the chew. The record should be written before the participants start the chew.

Trigger management worksheet (Appendix E) is a worksheet of self control strategies that one can abide with to manage their trigger situation. In a single day, participants can experience many and varied types of triggers that lead them to chew. During the intervention, participants will only be encouraged to manage (intervene) in two or three triggers in a week. This gradual approach is so that participants can cope with the withdrawal symptoms that results from these small changes. Participants will be guided on how to systematically decide on the subtle strategies to adopt. The worksheet will contain all strategies used and advocated by the participants. Chewers will be guided to tackle the easiest trigger situations first before moving to the more difficult situation. As chewers have a good sense of which situation they are more capable to intervene, they should be consulted first before the prescription of the trigger management strategies.

Arecoline fading concept and worksheet (Appendix F) is a worksheet that utilises the concept of gradually reducing the participant's physical dependence on AN. This worksheet will serve as a guide to perform the rate reduction method prior to the quit date. Participants will be advised to reduce 1 quid in a day for 2-3 days or at a rate of reduction of 10% consumption in 2-3 days. By adhering to this rate reduction method through a close monitoring from the worksheet, participants will be able to reduce the intensity of their

withdrawal symptoms on the quit day and this will make their quitting experience less difficult. This fading concept too could be a good substitute for pharmacological approaches.

Lifestyle Change worksheets will assist the participants to make lifestyle changes which are crucial for one to remain abstinent. There are 6 questions in the **Non-Chewing Game Plan : Lifestyle Change Worksheet (Appendix I)**. The questions revolve around the lifestyle changes that the participants can make to assist them to quit the habit; namely “What will you do to make betel quid unavailable to you”, “What will you do to increase time spent in non-chewing areas or doing non-chewing activities”, “How can you get help from others while trying to quit”, “What will you do to manage stress successfully”, “What will you do from keeping from gaining weight” and “What will you do to be physically active”.

[figure not shown]
Non- Chewing Game Plan : Coping with High Risk Situation Worksheet (Appendix J) is another lifestyle change worksheet that are targeted to prepare participants for potential high risk situation that they may experience in their community and daily lives. For each specific high-risk situation that they participants can identify, description of the event, persons that they might be with, what were they doing, thinking, or feeling at the time will be asked to be recorded in the worksheet. Participant will be asked to develop and record a full set of coping strategies to deal with their situation so that they could remain not chewing in such environment. They are required to utilise the 3As (Avoid, Alter, use Alternatives) of coping mechanism skills and document it in this worksheet. This worksheet really aids in their efforts to replace chewing behaviour to an abstinent one.

Social Support for Non Chewing Worksheet (Appendix K) is a tool to maximise the social support of the participant to quit the behaviour. Social support can be a good source

of motivation and may also act as a buffer for stressful situations. Thus, they are required to identify and record behaviours of others that are helpful and not helpful in their non-chewing efforts, and also activities that the participants would like others to increase or decrease to help participants in the their journey of quitting chewing.

Positive and Negative Thoughts Worksheet (Appendix L). In this worksheet, the participants will be asked to keep track of their positive and negative thoughts throughout the intervention. Thoughts which contain clear message of positivity or negativity should be recorded. Later, participants will be asked to record a self technique to increase their positive thoughts and a self technique to reduce their negative thoughts and how effective it was for them.

The questionnaire, educational booklet and intervention module will undergo adaptation process through ADAPT framework (Moore G et al. 2021) as below:

[figure not shown]

3.10.1.4 Questionnaire, Educational Booklet and Intervention Module Validation

The questionnaire, educational booklet and intervention module will be set in English and face validation will be undertaken by researchers. Later it will be submitted to smoking cessation experts from Department of Social and Preventive Medicine and Centre of Addiction Science, Universiti Malaya for content validation.

The experts will be required to review questionnaire, educational booklet and intervention module items for clarity and appropriateness based on the study's intended objectives. A further necessary modification will be undertaken after obtaining the comments and suggestions.

In summary, the content validation procedure will include 6 steps (Yusoff MSB, 2019) as below:

3.10.1.5 Questionnaire, Educational Booklet and Intervention Module Translation

The validated questionnaire, educational booklet and intervention module will later undergo an independent forward-backward translation. Firstly, the validated material (source) will be independently translated using a forward translation technique to the target language '*Bahasa Melayu*' (the national language) by two bilingual linguistic experts. The linguistics will later meet to review their translation together to search for inconsistencies with the original English set. Any difference of opinion will be resolved via reconciliation process, to come out with a single provisional forward translation.

The translated questionnaire, educational booklet and intervention module will then be independently back-translated to English by another two bilingual linguistics. They will compare the back translation and the original form of questionnaire for semantic equivalence. Semantic equivalence is a declaration that two data elements from different vocabularies contain data that has a similar meaning. This will ensure that the provisional forward translation is adequate representation of the original English set.

3.10.2 Phase 2 Pre-Test and Pilot Test

3.10.2.1 Pre-Test

The forward translation will then be pretested among 8-10 participants from a Bajau community in Kota Belud, Sabah, which will not be selected as the sample of the field study. This cognitive debriefing (pretest) will help to assure the clarity and non-ambiguity of the questionnaire to both the interviewer and subject. This will later allow for cross-cultural adaptation of the questionnaire in terms of conceptual and operational equivalence. Pretesting helps in ensuring that questionnaire is valid and could smoothly be administered to the

participants. A face-to-face interview will be carried out by the main researcher and the duration of each interview will be kept to below 30 minutes.

3.10.2.2 Pilot Test

Once modification from the pretest findings have been done, a subsequent pilot test will be done on the questionnaire, educational booklet and intervention module to assess its feasibility and psychometric properties. The pilot test will include close to 20-30 participants; again those who will not be selected as samples of this study or samples from the pretest. Later, the internal consistency of the items will be assessed to determine its reliability.

A focus group discussion will be utilised to garner patient's feedback of the intervention program. Questions such as language use, length of intervention and duration of each session, clarity and usefulness of the worksheet in creating awareness and suggestion for improvement will be obtained from participants.

Prior to the conduct of the pilot test, the participants will be briefed regarding the purpose of the study and will be provided with a 'Patient Information Sheet (PIS)' (Appendix A) that will contain the study information. A written consent too (Appendix B) will be obtained from the participants prior to the pilot test.

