Pankaj C. (2010) stated feasible **environmental access** to BQ is a sociological concern especially if BQ is readily available in a person's surroundings; as it is closely associated with its use. The study showed that there was four environmental promotion factors found in Malaysia; **easy availability, low cost, ready-made packaging and attractive packaging** and **no preventive activities reported in the country**; namely BQ-related ban, statutory warning and health education awareness programmes. Only Taiwan had practiced all the 3 preventive activities evaluated in the study (Lee CH et al., 2012).

Approaches such as Diagnostic and Statistical Manual of Mental Disorders (DSM; American Psychiatric Association, 2000) and the ICD-10 (World Health Organization, 1992)

were the common tools used in dependency studies for BQ. Both tools only involved the generic assessment of dependence among the BQ chewers.

In 2012, Lee CY et al. developed and provided an initial validation for the first instrument designed specially for measuring the BQ dependence; the Betel Quid Dependence Scale (BQDS). The BQDS was comprised of 3 domains; physical and psychological urgent need, increasing dose and maladaptive use. The instrument had a good internal consistency ($\alpha=.92$) and construct validity. Good construct validity represents how well the ideas or theories are translated into actual programs or item measures. Nevertheless, there was limitation to this first scale as it was developed among male prisoners who had history of BQ chewing before being incarceration in Taiwan prisons and items was evaluated in Chinese language. In 2014, Herzog TA et al. replicated and extended the validation research on BQDS among English speaking male and female current chewers in Guam.

Guam is an island in Micronesia which was situated close to Philippines and East Malaysia (Figure 2.1). Due to their proximity, they shared similar cultural history and tropical marine climate. Thus, this BQDS scale can be utilised to evaluate the dependency level among BQ chewers in the high risk group in Sabah for this study as they share some similar characteristics.

Figure 2.1 Map of Guam and Its Proximity to East Malaysia

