3.14 Data Collection

3.14.1 Baseline

The facilitators from the Kota Belud Dental Clinic staff will be trained and standardised for the conduct of this study. A training manual will be given to each facilitators. They will be briefed and their understanding on every item of the questionnaire and worksheets will be scrutinised and refined as intended by the study. Any difficult words identified by the facilitators will be changed to a simpler alternative. Translated words into Bajau dialect will be discussed and decided upon for standardisation.

From face-to-face interviews with the participants, information regarding demographics details and baseline information about BQ chewing behaviour, BQ composition, BQ dependency levels, reasons for chewing and readiness and self-perceived barriers to quit will be garnered. Face-to-face interview mode was chosen as a method to complete the questionnaire to obtain a better response rate and to minimise inaccurate response due to illiteracy issues and participant's poor comprehension due to age.

Participant's baseline saliva samples will be gained for biomarker comparison as a method to verify the intervention's self-reported effectiveness. Saliva samples collected will be transported within 2-3 hours to the lab facilities to be stored under -80 °C temperature. The transportation of these saliva samples will be monitored and carried out by the main researcher.

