3.15.2 Data Entry

All data collected will be entered into a Microsoft Excel database, cleaned and then exported to Statistical Package for Social Sciences (SPSS) version 29.0. Descriptive analysis through means and standard deviation will be reported for continuous variable and in the form of percentage for categorical variables and individual items in each domain. A mean and standard deviation also will be calculated for the aggregated domain score. Data of participants that attended all sessions will be analyzed for the cessation rate measurements.

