
Training of the Main Researcher
 
1. Questionnaire Design and Validation Workshop ~
 
2. Kuala Lumpur Nicotine Addiction International Conference
 
3. Qualitative Research Methodology & Data Analysis Using Atlas Ti V22 Workshop
 
4. Effective Thesis Writing
 
5. Cognitive Behavioural Therapy (CBT) on Substance Abuse
 
6. One-to One Training with BENIT Principal Researchers (AP [name] & AP [name])
	
29th September 2022
 
3rd October 2022
 
12-13th November 2022
 
29th & 30th November 2022
 
29th & 30th November 2022
 
April 2023
	
Completed
 
Completed
 
Completed
 
Completed
 
Completed
 
In Progress

Phase 2
 
Village selection & recruitment (Inclusive of meeting with village head for Pre-test Village)
 
Pre-test
	
May 2023 (Week 1)
 
May 2023 (Week 2)
	

Activities	Dates	Progress
Recruitment & Training of the Facilitators	May 2023 (Week 3)	
Meeting with Village Head & Preparation for Pilot Test	May 2023 (Week 4)	
Pilot test	June 2023 (Week 1-3)	
Modification to the Questionnaire, Educational Booklet, Intervention Module & others based on findings of Pilot Test	June 2023 (Week 4)	
Training of the Facilitators	July 2023 (Week 1)	
Phase 3 Promotional Initiatives	July 2023 (Week 1)	
Implementation of the study & Field Data collection	July-September 2023	
Data entry	October 2023 (Week 1-2)	
Data analysis	October 2023 (Week 3-4)	
Report writing	November-December 2023	
Candidature Defence	January 2024	
Manuscript writing	January 2024	
Report submission	February-March 2024	

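### Scale reliability is determined only in a 20-30 person pilot, and questionnaire changes follow with no re-test, so the figure may not describe the version used and may be imprecise

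*Protocol*

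**What the plan says.** Section 3.10.2.2 of the protocol sets the size of the pilot ("The pilot test will include close to 20-30 participants"), draws its participants from outside the trial and the pre-test, and assigns it the reliability assessment: "Later, the internal consistency of the items will be assessed to determine its reliability". Section 3.3 allots one village to the pilot. Pre-test changes are made before the pilot ("Once modification from the pretest findings have been done, a subsequent pilot test will be done on the questionnaire, educational booklet and intervention module"), so they do not affect the reliability figure.

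Section 3.25 puts the pilot in June 2023, weeks 1-3. Week 4 is set aside for "Modification to the Questionnaire, Educational Booklet, Intervention Module & others based on findings of Pilot Test". Facilitator training and implementation follow in July, and no re-test is listed. Section 3.14.1 adds that "Any difficult words identified by the facilitators will be changed to a simpler alternative", without a date.

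The items are in section 3.15.1 and Appendix C, all answered yes or no. The reasons scale has constructs of 2, 4 and 4 items; the dependence scale has domains of 7, 5 and 4. Section 3.15.2 plans percentages for individual items and then: "A mean and standard deviation also will be calculated for the aggregated domain score". It plans no reliability estimate from trial data.

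**The concern.** A reliability coefficient belongs to a particular set of items, in a particular wording, asked of a particular group. Here the protocol names the pilot as the sample that determines it, then leaves room to change the questionnaire before the trial starts. If scale items are reworded in that step, the coefficient describes a version that the trial does not use.

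The pilot is also small for domains of 2 to 7 binary items. A coefficient in the middle of the range would come with an interval too wide to separate a usable domain from a poor one, yet domain means and standard deviations are to be reported.

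At stake is how far readers can trust the dependency-level summary in objective i and the reasons-for-chewing summary in objective ii. The same items will be asked at baseline, in final wording, of every enrolled participant, so a better estimate is available from data already being collected.

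**Working it through.** **Order of events (sections 3.10.2.2, 3.14.1, 3.25).**

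1. Pre-test, then changes.
2. Facilitator training, May 2023, week 3.
3. Pilot, June, weeks 1-3. Internal consistency is assigned to this stage.
4. Modification based on pilot findings, June, week 4.
5. Facilitator training again, July, week 1.
6. Trial, July to September.

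Step 4 comes after the only reliability estimate. The undated word changes of 3.14.1 could fall at step 2 or step 5.

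**Inputs for precision.** Pilot size is 20-30 (3.10.2.2); 25 is the midpoint. Domain sizes k are 2, 4, 5 and 7 (3.15.1). The protocol gives no basis for 20-30 and no target coefficient, so there is no stated precision to reproduce. The trial size in 3.4 does reproduce: 38 per arm x 1.2 = 45.6, rounded to 46, and 2 x 46 = 92. Baseline interviews precede dropout, so 92 is the relevant number. The observed coefficient is an assumption. I use 0.70 and then vary it, because the documents give no expected value for the translated scales.

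**Formula (Feldt 95% interval).** With observed coefficient a, n people and k items, take F on n-1 and (n-1)(k-1) degrees of freedom:

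lower = 1 - (1-a) x F(0.975); upper = 1 - (1-a) x F(0.025)

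**At a = 0.70** (limits from unrounded F):

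| n | k | df | F(0.975) | F(0.025) | 95% interval | width |
|---|---|---|---|---|---|---|
| 25 | 2 | 24, 24 | 2.269 | 0.441 | 0.32-0.87 | 0.55 |
| 25 | 4 | 24, 72 | 1.841 | 0.486 | 0.45-0.85 | 0.41 |
| 25 | 7 | 24, 144 | 1.740 | 0.501 | 0.48-0.85 | 0.37 |
| 92 | 2 | 91, 91 | 1.512 | 0.661 | 0.55-0.80 | 0.26 |
| 92 | 4 | 91, 273 | 1.381 | 0.704 | 0.59-0.79 | 0.20 |
| 92 | 7 | 91, 546 | 1.346 | 0.717 | 0.60-0.79 | 0.19 |

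Worked example, n = 25 and k = 2: 1 - 0.30 x 2.269 = 0.32; 1 - 0.30 x 0.441 = 0.87. For 2 items the interval is 0.24-0.88 at n = 20 and 0.37-0.86 at n = 30.

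**Varying the coefficient at n = 20 (lower limits).**

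- a = 0.80: 0.49 (2 items), 0.60 (4), 0.63 (7).
- a = 0.92: 1 - 0.08 x 2.526 = 0.80 (2 items), 0.84 (4), 0.85 (5), 0.85 (7), and 0.86 for the full 16-item dependence scale.

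**Check on binary items.** The formula rests on normal theory, so yes/no items were also simulated. With 4 items and a population value of 0.70, the central 95% of estimates ran 0.33-0.87 at n = 20, 0.44-0.84 at n = 30 and 0.58-0.79 at n = 92, a similar spread.

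**The case against.** Revising materials after a pilot is what a pilot is for, and a reliability estimate on trial data could be left to a statistical analysis plan, which is not at hand. The first part stands. The second stands only in part: the protocol does more than stay silent, because it names the sample that determines reliability.

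A reader might infer that the pilot figure cannot describe the trial questionnaire. The documents do not support that. The modification depends on pilot findings and also covers the booklet and the module. The focus-group feedback in 3.10.2.2 concerns mainly the intervention, so scale items may change little or not at all. The word changes in 3.14.1 may come before the pilot, since facilitator training is listed both before and after it.

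A reader might also infer that a pilot of this size can never tell an acceptable scale from a poor one. That too goes beyond the evidence. The one coefficient in the protocol, in section 2.5, is high ("The instrument had a good internal consistency ($\alpha=.92$) and construct validity"), and at 0.92 even 20 people would suffice. However, that value is for the whole dependence scale in Chinese among male prisoners in Taiwan. It is not a domain value, not for Malay or Bajau wording, and not for the reasons scale, so it cannot be assumed here.

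Finally, 92 people do not settle every case. At an observed 0.70 the intervals still start between 0.55 and 0.60. Precision roughly doubles, but some ambiguity remains.

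**Conclusion.** The point holds in limited form. The pilot is the only place where the protocol assesses reliability, questionnaire modification is scheduled after it, and no re-test is listed. The pilot figure therefore may not describe the trial version. It will also be imprecise if the coefficient is middling or the domain short: at an observed 0.70 and n = 25, the intervals are 0.37 to 0.55 wide. It would be adequate if the coefficient is near 0.92.

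These sizes rest on an assumed observed value, a normal-theory interval applied to binary items, and independent respondents. The baseline sample comes from four villages (tentatively, section 3.3), so its true intervals could be somewhat wider than shown.

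The reach is narrow. It might be supposed that objectives i to iii all rest on these scores; section 1.6.2 does not bear that out. Only dependency level in objective i and reasons for chewing in objective ii use the scales. Readiness and barriers are separate items, objective iii is the adaptation of the programme, and neither self-reported quitting nor the sample size depends on scale reliability. This is a low-cost improvement to two descriptive summaries.

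**What to change.** - **Section 3.10.2.2:** state that the pilot coefficient is provisional and serves to guide revision of the questionnaire.
- **Section 3.15.2:** state that internal consistency (KR-20 or alpha, with a 95% confidence interval) is computed for each reasons-scale construct and each dependence-scale domain from the baseline interviews of all enrolled participants, about 92, in the final wording, and that this is reported as the reliability of the adapted instrument. Mention village clustering as a caveat to the interval.
- **Where a domain is not consistent:** rely on the item percentages already planned in 3.15.2 rather than on the domain mean and standard deviation.

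The cost is a few lines of analysis and a sentence or two in each section, with no new participants, visits or data. The downside is that the reported value may be less favourable than the pilot's.
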